IVFE reduction (IFER) during the administration of neonatal parenteral nutrition will lead to a significant decrease in the rate of rise of direct bilirubin (mg/dL/week) when compared to standard therapy.

Secondary Hypotheses

1. The time to development of PNAC, when present, will be longer with IFER when compared to standard IVFE therapy.
2. IFER will not be associated with a significant increase in failure to thrive (as assessed by growth parameters) or the development of essential fatty acid deficiency (EFAD) when compared to standard IVFE therapy.
3. Neurodevelopmental outcomes (NDOs), when assessed at 12 and 24 months of corrected gestational age, will be similar for those treated with IFER and standard IVFE therapy.

Specific Aims

1. To determine whether neonates and infants receiving PN with IFER (1 g/kg/day) will have lower rates of rise of direct bilirubin compared to those receiving standard IVFE therapy (3 g/kg/day)
2. To compare the time to development of PNAC in neonates and infants receiving PN with IFER (1 g/kg/day) compared to those receiving PN with standard IVFE administration (3 g/kg/day)
3. To determine if IFER results in normal growth and essential fatty acid (EFA) parameters by measuring weight, length, head circumference (weekly) and EFA profiles (every 2 weeks in the IFER group) during the treatment period.
4. To compare NDOs at 12 and 24 months of corrected gestational (± 2 weeks) age of those treated with IFER with those treated with standard IVFE doses using a combination of neurodevelopmental screening tools (e.g. Bayley Scales of Infant Development, MacArthur Communicative Development Inventory, etc.) aimed at capturing several developmental domains such as motor, cognition, speech and language, sensory, and behavior.

Study Definitions

Subjects will be considered “on treatment” from the time of randomization until 7 days after PN has been discontinued, but not to exceed a total of 84 days. Subjects will be considered “on study” until they complete their neurodevelopmental testing at 24 months corrected gestational age (± 2 weeks).

Study Design

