1. If TG are <250 mg/dL: restart IVFE at 50% of previous dose
2. If TG are ≥250 mg/dL: continue to hold IVFE infusion and repeat TG level every 48 hours until <250 mg/dL. If IVFE is held for ≥7 days with continued TG levels ≥250 mg/dL, restart IVFE at 0.5 g/kg/day

Essential Fatty Acid Deficiency (EFAD)

The detection of EFAD will be assisted by a biochemist and expert in the area of lipid biology.

The IVFE dose will be adjusted if subjects develop EFAD. EFAD will be defined by the development of any of the following:

1. Clinical evidence of EFAD deficiency (i.e. scaly skin)^{31,32}
2. Triene:tetraene ratio of >0.20
3. Arachidonic acid (ARA), (EPA) and/or docosahexaenoic acid (DHA) levels below normal as defined by Mayo Laboratory reference ranges

In the presence of EFAD, the IVFE dose will be increased in 0.5 g/kg/day increments based on biweekly essential fatty acid profiles until resolved.

Cycled Parenteral Nutrition

Study subjects will not receive cycled parenteral nutrition (i.e. parenteral nutrition administered over less than 24 hours per day) during the study period, as cycled PN has been shown to decrease the development of PNAC and may represent a confounder.^{33,34}

Adjustment of Parenteral Nutrition if Inadequate Weight Gain Occurs

(Lipid Restricted Group Only)

Subjects with inadequate weight gain that cannot be attributed to other physiologic causes (e.g. low urine sodium, low hematocrit, insufficient respiratory support) will be managed according to the protocol described below.

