Indicators of acute and chronic malnutrition will be assessed using z-scores.³⁵ For the purposes of the initial 12 weeks, subjects will only be assessed for **acute** malnutrition as chronic malnutrition occurs after 3 months. Z-scores will be obtained using the Peditools.org calculator (<https://peditools.org/>). Fenton scores³⁶ will be used for infants born <37 weeks gestation, until 50 weeks gestation, at which time the WHO scores will be used, using corrected gestational age. WHO scores³⁷ will be used for infants born at ≥37 weeks gestation. Z-scores will be documented for birth anthropometrics. Z-scores will be assessed at 1 month of age and weekly thereafter (allowing 1 month before reassessment to account for natural weight loss at birth in addition to weight loss from acute illness at birth). Z-scores for all anthropometrics will be followed, however, the z-score for weight-for-age will be used as the primary assessment for acute malnutrition and will be used to prompt intervention. If intervention is required, PN will be adjusted as described in **Table 1**.

Table 1. PN Adjustments Based on Change in Z-score (after 1 month of age)

Decrease in z-score by 0.5 standard deviation (SD) (17 percentiles decrease) from birth	Increase DIR by 2 mg/kg/min (as clinically tolerated) Maximum DIR for study subjects 0 – 30 days old: 16 mg/kg/min Maximum DIR for study subjects >30 days old: 18 mg/kg/min
Decrease in z-score by 1 SD (34 percentiles decrease) from birth	1. Increase DIR by 2 mg/kg/min (as clinically tolerated)

	
 a. Maximum DIR for study subjects 0 – 30 days old: 16 mg/kg/min b. Maximum DIR for study subjects >30 days old: 18 mg/kg/min 
 2. If Z-score is not improving in response to increase in DIR after 1 week, or if DIR is already at max of 18 mg/kg/min, increase IVFE by 0.5 g/kg/day to a maximum of 1.5 g/kg/day 3. If poor weight gain continues and consideration is being made to increase the lipid dose to 2 g/kg/day the coordinating center must be contacted to determine if the subject should be withdrawn.
Decrease in z-score by 2 SD from birth x2 consecutive measurements separated by 7 days or Lipids need to be increased to >1.5 g/kg/d d/t poor growth	Subject deemed to have growth failure, prompting exit from study in order to allow for liberalization of the IVFE dose to promote adequate growth

Data Collection

1. Demographic information
2. Birth weight, gestational age

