3. Weight, gestational age at the time of enrollment/randomization, and weekly thereafter
4. Inclusion diagnosis
5. Number of septic episodes according to standard definitions³⁸
6. Use of choleric medications
 - a. Ursodiol
 - b. Cholecystokinin
 - c. Phenobarbital
7. Nutritional data
 - a. Parenteral nutrition data
 - i. IVFE dose
 - ii. Dextrose infusion rate
 - iii. Total calories and % calories obtained via PN
 - b. Enteral nutrition data
 - i. Total calories and % calories being obtained via enteral route
 - ii. % calories obtained via breast milk
8. Growth parameters (whenever possible, obtain all growth measurements on the same day of the week)
 - i. Weight (with z-score) weekly (every 7 days ± 2 days)
 - ii. Height (with z-score) weekly (every 7 days ± 2 days)
 - iii. Head circumference (with z-score) weekly (every 7 days ± 2 days)
9. Additional safety data to be obtained from human subjects is summarized below, indicating any key differences in frequency of monitoring between the two groups:

Laboratory Parameter	Frequency (+24 hours)*
Fractionated bilirubin panel (includes total, indirect, and direct bilirubin)	One time weekly (Monday)
Serum bile acids (total)	One time monthly (every 4 th Monday on treatment)

Point of care or serum glucose measures	- Daily for the first 5 days of PN, then twice weekly (Monday, Thursday) - Confirmatory test if serum glucose is >150 mg/dL on electrolyte panel
Serum Triglycerides	One time weekly (Monday)
Essential Fatty Acid Profile	IFER Group: Every 2 weeks (Thursday) Standard Group: At the time of restriction of IVFE to 1 g/kg/day three days per week, then every 2 weeks (Thursday)
Comprehensive metabolic panel	Twice weekly (Monday, Thursday)
Magnesium level	Twice weekly (Monday, Thursday)
Phosphorus level	Twice weekly (Monday, Thursday)
Complete blood count	One time weekly (Monday)

* Lab draw volumes will be below each institution's daily limits

Definition of Sepsis

Sepsis will be defined in a standard manner using the following criteria (**Table 2**):³⁸

The presence of at least two of the following four criteria ***in the presence of or as a result of suspected or proven infection***:

1. Core temperature of >38.5C or <36C

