These measures will be compared between the two treatment groups using a linear mixed model.

3. Incidence of PNAC, severe PNAC, and EFAD

The number of occurrences of each of these outcomes will be compared using either a Poisson regression model or a negative binomial model if the variance in these counts is greater than expected for a Poisson distribution. We will also include the time on TPN as an offset, so that we can compare the rates of occurrence of each of these outcomes for the two treatment groups. These regression models will be adjusted for the covariates such as development of sepsis, average IVFE dose, and percentage of enteral feeds.

4. Adequacy of growth as evaluated by z-scores for weight, height and head circumference

The z-scores for each of these measures will be compared between the two treatment groups using a linear mixed model. For normally growing infants, we would expect that there would not be a trend in z-scores because we would expect them to maintain their curve. However, for the subjects in this study, there may be a loss in z-score over time due to inadequate growth. The slopes of the changes in these z-scores over time will be compared between the two treatment arms. A random intercept will be included for each subject to allow for individual variability in average values as well as a random slope to allow for variability in the rate of change over time across subjects. Important covariates, such as gestational age (<32 weeks gestation vs. ≥32 weeks gestation) and birth weight will also be used as covariates in this analysis.

5. Neurodevelopmental Outcomes

Bayley Scales of Infant and Toddler Development (BSID-III):⁴⁵ Raw scores are converted to composite and subscale scores using age-standardized norms. Scale composite average internal consistency reliability coefficients range from .91 to .93 with subtest reliability ranging from .86 to .91. Validity-related studies indicate relatively high correlations (.72-.79) with the Wechsler Preschool and Primary Scale of Intelligence – Third Edition (WPPSI-III)⁵³ and with the Preschool Language Scale – Fourth Edition (PLS-4)(.71-.83).⁵⁴

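### Weight z-score triggers growth rescue in the IFER arm only and is also the growth outcome, so the slope comparison tests IFER with rescue and understates any growth harm of 1 g/kg/day itself

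*Combined protocol and SAP*

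**What the plan says.** - **Hypothesis.** Secondary Hypothesis 2 states that "IFER will not be associated with a significant increase in failure to thrive (as assessed by growth parameters", and goes on to essential fatty acid deficiency. It gives no margin.
- **Who is rescued.** The section Adjustment of Parenteral Nutrition if Inadequate Weight Gain Occurs carries the restriction "Lipid Restricted Group Only".
- **Trigger.** In that section, "the z-score for weight-for-age will be used as the primary assessment for acute malnutrition and will be used to prompt intervention". On timing, "Z-scores will be assessed at 1 month of age and weekly thereafter".
- **Steps (Table 1).** The first row is "Decrease in z-score by 0.5 standard deviation (SD) (17 percentiles decrease) from birth", which raises the dextrose infusion rate. At 1 SD the dextrose rate rises and then, without a response or at the dextrose maximum, the instruction is to "increase IVFE by 0.5 g/kg/day to a maximum of 1.5 g/kg/day". A fall of 2 SD on two measurements 7 days apart, or a need for more lipid than that maximum, means growth failure and exit.
- **Regimen.** The IVFE guideline for the IFER arm holds the dose at 1 g/kg/day except for inadequate growth or fatty acid deficiency.
- **Analysis.** Secondary Outcome Measures, item 4: "The slopes of the changes in these z-scores over time will be compared between the two treatment arms". The model is a linear mixed model with random intercept and slope. Gestational age and birth weight are the named covariates. Nothing is said about values after rescue or exit, and no listed outcome counts rescue.

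**The concern.** The outcome variable starts its own correction, in one arm only. A standard-arm infant with the same fall in z-score has no corresponding rule. If the extra dextrose or lipid works, the IFER slope is pulled up and the difference between arms shrinks. That is the result the hypothesis predicts, and without a margin a non-significant difference would be read as support for it.

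The possibility is not remote. In the randomized pilot of the same two doses described in the background, weight z-scores increased more in the standard group (p=0.006), although average daily gain was similar (23.7 versus 20.8 g/day). Item 4 itself expects that z-scores may fall. An infant rescued after a fall of 0.5 to 1 SD appears in no listed growth outcome except through the slope that rescue has altered. At stake is what the trial may say about the growth safety of a lower lipid dose in neonates.

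**Working it through.** The plan states no effect size, variance or power for growth, so there is no figure of its own to reproduce. The direction follows from the text. The size has to be illustrated with assumptions.

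**From the documents:** weekly z-scores in both arms; a 12-week period; rescue from 1 month of age at a 0.5 SD fall from birth, IFER arm only; slopes compared between arms.

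**Assumed (set A):** linear z-scores from birth, so that 1 month is week 4; slopes of -0.04 per week (standard) and -0.08 (IFER), a true difference of -0.040; between-infant slope SD 0.04; measurement SD 0.15; every observed fall of 0.5 SD leads to rescue. A least-squares slope is fitted to each infant in large simulated arms.

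Attenuation = 1 - (measured difference / true difference).

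| What rescue does after the trigger | Measured difference (z/week) | Attenuation |
|---|---|---|
| No rescue | -0.040 | 0 |
| Cancels half the assumed harm | -0.031 | 1 - 0.031/0.040 = 22% |
| Cancels exactly the assumed harm | -0.023 | 1 - 0.023/0.040 = 43% |
| Resets to the average standard slope | -0.014 | 1 - 0.014/0.040 = 65% |
| Stops the fall altogether | +0.003 | all of it |

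The last two rows are generous to rescue. Rescued infants are selected for steep decline, so resetting them to an average or zero slope also removes ordinary variation between infants.

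**Sensitivity of set A.** With a flat standard arm (slope 0), exact cancelling gives about -0.031 (22%) and half cancelling about -0.036 (10%). With PN stopping at varying times between weeks 4 and 12, exact cancelling gives -0.029 to -0.032 (27% to 20%), depending on how the stopping times are spread, and half cancelling gives -0.035 to -0.036 (12% to 10%).

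**Set B (also assumed):** 20 infants per arm; standard slope -0.04; true harm 0.05 per week; between-infant SD 0.05; measurement SD 0.15; t-test on slopes. Rescue percentages are the share of the decline removed at the 0.5 and 1 SD triggers.

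| Rescue | Difference | Detected at 0.05 |
|---|---|---|
| None | -0.049 | 86% |
| 25% / 50% | -0.034 | 63% |
| 50% / 75% | -0.021 | 38% |
| 100% | +0.003 | 6% |

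With a flat standard arm in set B, the difference goes from -0.049 to between -0.044 and -0.025, which is 10% to 49% attenuation. In every scenario tried the difference moved toward zero.

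**What rescue cannot alter.** The share reaching the first 0.5 SD fall is fixed before rescue acts. In set A it is 59% (standard) and about 88% (IFER) in every row. It can saturate, however. If both arms lose 0.6 SD early (assumed), 88% versus 97% are past the threshold at week 4, and 98% versus nearly 100% by week 12.

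**Related wording.** Under Study Arms, infants with direct bilirubin of at least 2.5 mg/dL for two consecutive weeks move to 1 g/kg on three days a week: 1 x 3 = 3 g/kg/week, against 1 x 7 = 7 g/kg/week on assigned IFER. The laboratory table extends fatty acid profiles to switched standard infants ("Standard Group: At the time of restriction of IVFE to 1 g/kg/day three days per week"). The growth section does not say whether its restricted group now includes them.

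**The case against.** The strongest reply is that rescue belongs to the assigned regimen. The IFER guideline names inadequate growth as a reason to change the dose, so intent to treat compares two strategies as they would be used. This stands, and the slope should stay. But Specific Aims 1 and 2 describe IFER as 1 g/kg/day, and the plan never says which question Hypothesis 2 answers.

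Partial safeguards also stand. Length and head-circumference slopes are compared and trigger nothing. A fall of 2 SD or more is a listed adverse event in either arm. Dextrose goals and limits apply to both arms, and undernutrition that cannot be managed is a general removal criterion. Falls with another physiologic cause are exempt from Table 1, and dextrose increases depend on tolerance, so not every fall leads to rescue. Using mean IVFE dose as a covariate (Potential Confounding Variables) does not help: it is measured after randomization, nearly duplicates the arm, and ignores dextrose.

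Three stronger readings are tempting but unsupported:

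- *The IFER slopes are mostly post-rescue data.* Under set A only about 39% of IFER values follow the first trigger, and fewer if PN stops early.
- *Rescue hides the harm.* Complete masking needs a rescue that stops the decline entirely, and the documents give no rescue effect.
- *Switched standard infants are the least lipid-supplied in the trial.* The bilirubin switch applies to both arms, so switched IFER infants also receive 3 g/kg/week.

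**Conclusion.** The concern holds as a limit on what the growth comparison can show. The weight z-score slope estimates IFER with growth rescue against standard dosing without it. For 1 g/kg/day itself, the result is biased toward no difference whenever rescue works. Illustratively, the loss is about 20% to 100% of a true slope difference, and nearer 10% to 27% if PN stops early or standard-arm growth is flat and rescue does no more than cancel the harm. All growth inputs are assumed; only the direction rests on the text. The effect of growth-failure exits was not sized, since at most about 1% of simulated infants exited. This is a secondary outcome, for which the sample size section promises trends only, but it carries the growth-safety claim and should be corrected.

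**What to change.** In Secondary Outcome Measures, item 4:

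1. Keep the slope comparison and state that its conclusion concerns IFER with growth rescue versus standard dosing. Do not conclude from the slope alone that 1 g/kg/day causes no growth harm.
2. In both arms, from the weekly z-scores already collected, report the proportion reaching and the time to 0.5, 1 and 2 SD below birth. Show infants already past a threshold at 1 month separately. Only the first threshold precedes all rescue; it is mild and may saturate, so it should not be the sole basis for the conclusion.
3. Add an analysis in which a growth-driven lipid increase or growth-failure exit counts as growth failure. By rule only IFER infants can have these events, so it leans against IFER, while the slope leans the other way. Read the two together.
4. Report growth-driven dextrose and lipid escalations and exits by arm.

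Separately, reconcile the growth section and Table 1 with Study Arms and the laboratory table on whether the restricted-group rules cover standard-arm infants after the bilirubin switch. No clinical rule is proposed here.

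The cost is wording and a few more secondary results. Z-scores, dextrose rate and lipid dose are already recorded, but the data collection list names no reason for a change, so the form may need one added field.

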 - iii. Brief Infant Toddler Social Emotional Assessment (BITSEA)
 - iv. Gross Motor Function Classification System (GMFCS)
 - v. Behavioral Assessment System for Children-Second Edition (BASC2)

Study Arms:

[figure not shown]
Study Arm 1 (Standard IVFE dosing): Subjects in the standard IVFE dosing arm (3 g/kg/day) will be on treatment for a total of 12 weeks or until the subject has been off of parenteral nutrition for >7 days, or if they are discharged from the hospital, whichever comes first.

Study Arm 2 (IFER dosing): Subjects in the IFER dosing arm (1 g/kg/day) will be on treatment for a total of 12 weeks or until the subject has been off parenteral nutrition for >7 days, or if they are discharged from the hospital, whichever comes first.

All subjects will be maintained at their assigned dosing regimen for the duration of the treatment period (12 weeks) or until they are transitioned off of PN for >7 days, are discharged or until the direct bilirubin is ≥ 2.5 mg/dL for 2 consecutive weeks, whichever occurs first. Data will be collected for the duration of the study for those subjects who remain on parenteral nutrition for the full 12 weeks. For those who transition off of PN prior to the end of the 12 week period, data will be collected for 7 days after termination of PN if the subject remains in the hospital. The clinical course of these subjects who wean off PN prior to 12 weeks will continue to be monitored according to standards of practice. If serum direct bilirubin reaches a level of ≥ 2.5 mg/dL for 2 consecutive weeks during the course of the treatment, subjects will be transitioned to an IVFE dose of 1 g/kg/day three days per week. Those who remain cholestatic at the termination of their treatment period will be evaluated on a monthly basis for the persistence or resolution of cholestasis. This will be done by obtaining monthly liver function tests and bilirubin fractions for 6 months.

Overview of Study Design:

Study Design

Inclusion Criteria

Study subjects will be neonates and infants who are ≥ 28 weeks corrected gestational age at the time of enrollment who are parenteral nutrition naïve (<72 hours of PN exposure prior to randomization) and whose direct bilirubin has never been >2 mg/dL with at least one of the following diagnoses:

1. Meconium ileus and peritonitis
2. Gastroschisis
3. Omphalocele >4 cm in diameter or with liver herniated outside of the abdominal cavity

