Protein, in the form of neonatal IV amino acids solutions, will be initiated on the first day of PN at the highest delivery possible based on the following ranges:

Body weight:	<1.5 kg	1.5 – 2.5 kg	>2.5 kg
Protein Needs (g/kg):	3.4 – 4	3.2 – 3.8	2 – 3

If protein is not able to be initiated at the goals indicated above, protein will be advanced over the first 2-3 days of PN administration to reach specified goals.

In order to maintain uniformity in the PN administered between study centers, formulations will use neonatal-specific amino acid solutions that contain supplementation with taurine, glutamic acid and aspartic acid, all of which are not routinely contained in conventional adult crystalline amino acid infusions. Uniformity of amino acid solutions is particularly important because a lack of taurine may have a role in the development of PNAC.^{29,30} Ensuring that all infants receive this amino acid formulation will ensure uniformity between centers.

IVFE

Standard Arm: IVFE to begin at 1 g/kg/day on the first day of PN and advance by 0.5-1 g/kg/day to a maximum of 3 g/kg/day.

IFER arm: IVFE administration to begin and remain at 1 g/kg/day for the duration of the study unless inadequate weight gain/growth occurs and/or the subject develops EFAD.

Hypertriglyceridemia

If hypertriglyceridemia develops (serum triglycerides (TG)>250 mg/dL), subjects will be managed as follows:

1. Repeat laboratory measure to confirm diagnosis
2. Screen for carnitine deficiency (if present, supplement as appropriate)
3. If confirmatory TG >250 mg/dL, then:

TG 250-400 mg/dL AND glucose >150 mg/dL	TG 250-400 mg/dL AND glucose ≤150 mg/dL	TG ≥400 mg/dL AND glucose >150 mg/dL	TG >400 mg/dL AND glucose ≤150 mg/dL

 1. Decrease DIR by 1-2 mg/kg/min as tolerated until serum glucose normalizes 2. Decrease current IVFE infusion by 50% for the remainder of the current infusion 	
 1. Decrease current IVFE infusion by 50% for the remainder of the current infusion 2. Hold IVFE x 48 hours and repeat TG level* 	
 1. Decrease DIR by 1-2 mg/kg/min as tolerated until serum glucose normalizes 2. Discontinue current IVFE infusion 3. Hold IVFE x 48 hours and repeat TG level* 	
 1. Discontinue current IVFE infusion 2. Hold IVFE x 48 hours and repeat TG level*

3. Hold IVFE x 48 hours and repeat TG level*			
--	--	--	--

* Upon repeat TG level:

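### Table 1 sends IFER infants with growth failure to 'exit from study', and nothing says their 12- and 24-month neurodevelopmental tests continue; stop the assigned dose, not the follow-up

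*Combined protocol and SAP*

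**What the plan says.** The section on adjusting PN for inadequate weight gain is marked "Lipid Restricted Group Only". Its Table 1 sets graded responses to a fall in weight z-score from birth. The last row applies to a 2 SD fall on two measurements a week apart, or to a need for lipid above 1.5 g/kg/day because of poor growth. The instruction there is: "Subject deemed to have growth failure, prompting exit from study in order to allow for liberalization of the IVFE dose to promote adequate growth". In the 1 SD row, if 2 g/kg/day is being considered, "the coordinating center must be contacted to determine if the subject should be withdrawn".

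Study Definitions separates two states. An infant is on treatment "from the time of randomization until 7 days after PN has been discontinued, but not to exceed a total of 84 days", and on study "until they complete their neurodevelopmental testing at 24 months corrected gestational age". Neither definition depends on the lipid dose.

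Elsewhere 'study' is used more loosely. The IVFE section has the IFER dose "begin and remain at 1 g/kg/day for the duration of the study", and Study Arms says "Data will be collected for the duration of the study for those subjects who remain on parenteral nutrition for the full 12 weeks". Both plainly mean the 12-week phase.

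Secondary hypothesis 3 is that neurodevelopment at 12 and 24 months corrected age will be similar in the two arms. Neurodevelopmental Outcome Measures promises testing of study subjects in both arms, and the coordinator holds contact details for all participants. The analysis is intent to treat.

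**The concern.** The exit rule is triggered by poor growth, is written for one arm, and acts within 12 weeks of randomization. That is before any Bayley test, so the mixed model has no earlier score from an exited infant to draw on. If exit is applied as Study Definitions reads, the infants in whom lipid restriction went worst drop out of the one comparison meant to show that restriction does not harm development. If poor growth goes with poorer development, the IFER mean among those tested is too high. That error favors the hypothesis of similarity. Intent to treat governs who is analysed and in which arm; it cannot supply scores that were never collected. The plan gives no missing-data method for exits.

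**Working it through.** **1. Is exit needed to free the dose?** Three other rules change the lipid dose and do not call for exit.
- EFAD: the dose rises in 0.5 g/kg/day steps until resolved, with no ceiling stated.
- Cholestasis (direct bilirubin of at least 2.5 mg/dL for two consecutive weeks): the dose moves to 1 g/kg/day three days per week.
- Hypertriglyceridemia: lipid is halved or stopped, held, then restarted at a lower dose.

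Potential Confounding Variables also expects the dose to vary with clinical and nutritional status and plans to account for it. Liberalising the dose for growth can be handled the same way.

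**2. Does any section retain exited infants?** Data collection is spelled out for infants who wean off PN, who remain cholestatic, or who go home on PN. The section on removal from the study protocol lists reasons and describes no later follow-up. No section names infants who exit for growth failure.

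**3. Shift in the IFER mean if they go untested.** The documents give no exit rate, no Bayley SD and no growth–development correlation. Assumed: SD 15, r = 0.3 to 0.5, and the k lowest-growing of 30 infants are lost.
- Mean shift in growth, in SD units, on removing the k lowest of 30 standard normal values (simulated): 0.0705 for k = 1 and 0.1307 for k = 2.
- Shift in Bayley mean = growth shift × r × 15.
- k = 1: 0.0705 × 0.3 × 15 = 0.32, up to 0.0705 × 0.5 × 15 = 0.53 points.
- k = 2: 0.1307 × 0.3 × 15 = 0.59, up to 0.1307 × 0.5 × 15 = 0.98 points.
- Standard error of the arm difference with all 60 tested: 15 × √(2/30) = 3.87. The shift is therefore 0.32/3.87 = 0.08 to 0.98/3.87 = 0.25 standard errors.
- Two IFER losses against one standard-arm loss of the same kind: (0.1307 − 0.0705) × 15 × r = 0.27 to 0.45 points. Equal losses: 0.

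**4. What retaining them costs the primary outcome.** First, the plan's own figure. Least-squares slopes through the planned means at 0, 4, 8 and 12 weeks are 0.12125 (standard; the protocol quotes 0.125) and 0.0025 (IFER), a contrast of 0.11875 mg/dL/week. With SD 1 and the stated correlations, one infant's slope has SD 0.1008. At 20 per arm the standard error is 0.1008 × √(2/20) = 0.0319. A two-sided 5% t test then has 95.3% power; the protocol states 95%.

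Now let an exited IFER infant be flat to week w and then rise at the full standard-arm slope. Its least-squares slope over weekly values, weeks 0 to 12, is 0.0606 (w = 6), 0.0213 (w = 9) or 0.0040 (w = 11). These infants are still on PN when they exit, so they are counted among the 20 per arm left after the 33% attrition, which the protocol attributes to leaving PN. Loss of contrast = (k/20) × slope / 0.11875.

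| Exits | Week | Contrast lost | Power at 20 per arm |
|---|---|---|---|
| 0 | – | 0 | 95.3% |
| 2 | 11 | 0.3% | 95.1% |
| 2 | 9 | 1.8% | 94.6% |
| 2 | 6 | 5.1% | 93.1% |
| 5 | 6 | 12.8% | 88.6% |

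**The case against.** The strongest reply is that exit means only the end of the dosing phase. Table 1 concerns PN adjustment during the initial 12 weeks, its stated purpose is to free the dose, and the protocol often uses 'study' in that narrower sense. The promise to test subjects in both arms carries no exception, contact details are kept for everyone, and the analysis is intent to treat. The sponsor may well intend to test these infants. That much stands: the documents show an ambiguity, not a demonstrated loss of data. But the general text does not override an explicit exit instruction, and the only formal definition of 'on study' points the other way.

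A reader might infer three stronger things that the documents do not support.
- **That removal is wholly one-sided.** The Table 1 rule is, but item 3 of the general removal criteria permits discretionary removal for undernutrition in either arm.
- **That the 1 SD row and the last row contradict each other at 2 g/kg/day.** They can be read in sequence: consult the coordinating center when the increase is being considered, then exit if it is needed.
- **That the bias is large, or that its likely size is known.** No exit rate is given. A modelled rate would rest on assumed growth variability and would have to cover the second trigger (lipid above 1.5 g/kg/day) as well as the 2 SD fall. The randomized pilot described in the Background reports similar weight gain in grams per day, although weight z-scores rose more on the standard dose. Neurodevelopment is a secondary outcome, for which the protocol claims only to establish trends.

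**Conclusion.** The concern holds as a minor point. On the protocol's own definition, growth failure in the IFER arm ends follow-up before any neurodevelopmental score exists, and no section says otherwise for these infants. If they are lost, the error runs toward similarity. For 1 or 2 losses of 30 it is about 0.3 to 1.0 Bayley points, at most about a quarter of a standard error. That rests on the assumed SD of 15 and correlation of 0.3 to 0.5, and on the standard arm losing none. It shrinks with standard-arm losses and vanishes if losses are equal or if growth and development are unrelated. An open covariate list could admit growth and reduce the bias, but adjustment does not replace the missing scores. The case for acting rests on which infants would be lost and on how little it takes to keep them.

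**What to change.** Leave the clinical rescue as it is.
- In the last row of Table 1, replace 'exit from study' with *discontinue the assigned IVFE dose and remain on study*.
- In the 1 SD row, for consistency, have the coordinating center decide whether the assigned IVFE dose should be discontinued, in place of whether the infant is withdrawn.
- Add one sentence: *Scheduled growth, bilirubin and 12- and 24-month assessments continue, and these infants are analysed in their assigned arm.*

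This needs no new visits or measurements and no change to the sample size. If the sponsor already means to follow these infants, the edit only records it. The price is that some IFER bilirubin and growth data are collected on a liberalised dose. As tabulated above, that costs the primary comparison about 2 points of power or less for two exits, and about 7 points (95.3% to 88.6%) in the adverse case of five exits at week 6. An intent-to-treat analysis accepts that dilution.
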